Validation of PUFA Index in Assessing Untreated Dental Caries Among Malaysian Adult Subpopulation

RESEARCH PROTOCOL

10 September 2015

Introduction

Dental caries is considered a major factor of tooth ache and tooth loss in population all over the world (Fejerskov & Kidd 2003). In the year 2000, 90% of the adult Malaysian population had been reported to be living with caries (Oral health Division, Ministry of Health, Malaysia 2011). Dental caries in its advanced stages may influence the health and quality of life, causing pain, disturbances in sleeping patterns, eating difficulties, and reduced body weight (Jorge et al. 2014). In severe cases, it might even lead to hospitalization (Figueroa et al. 2011). In many developing nations, access to oral health service is extremely restricted and teeth are often left untreated or extracted because of pain or discomfort (Peterson 2003).

Traditionally, information on caries has been gathered by utilizing the DMFT index. The DMFT Index is expressed as the total number of teeth that are decayed (D), missing (M), or filled (F) in an individual. This established index provides information on the presence of caries, the restorative needs and any surgical intervention performed on a patient (Lamas 2010). The drawback of DMFT is that it fails to give information about the clinical outcomes of untreated dental caries. A deep caries cavity with pulpal involvement is still considered as decayed and pulpal involvement is not mentioned at all in the caries scoring system.

Hence, a new index was developed to record the full continuum of untreated dental caries. The PUFA index complements the DMFT index by recording the advancement of the caries lesion into surrounding tissues, including pulpal involvement (P), ulceration due to tooth fragments (U), fistula formation (F) and abscess (A) (Monse et al. 2010). Ideally, this index should reflect the underlying pulpal and periapical involvement of the carious lesion, thereby serving as a screening tool for further clinical and radiographic examinations to diagnose any pulpal and periapical diseases.

The PUFA index had been used in prevalence study among Philipino (Monse et al. 2010), Polish (Baginska et al. 2013) and Indian (Mehta & Sumatibhalia 2014) children. The reproducibility of the index was good, with intraexaminer kappa value of 0.85 and intraexaminer kappa values ranging from 0.80 to 0.97 (Monse et al. 2010). Despite that, currently the capability of the index in meeting the intended purpose of capturing the clinical sequelae of untreated dental caries was not assessed. This limits its use in triaging patients in a large practice, or in epidemiological survey (prevalence study) of a population. Therefore, it is paramount to ensure the index performs adequately as a screening tool when compare to conventional clinical procedures in disease detection. Furthermore, the PUFA index should also be tested in an adult population since the existing literature focused only on children.

Besides PUFA, variants of indices using the same concept were developed. In an attempt to simplify PUFA, Pulpal Involvement-Roots-Sepsis (PRS) Index was modified by redefining P as caries process reached pulp chamber, R as non-restorable caries. Also, Fistula and Abscess were combined as S (Baginska & Stokowska 2013). On the other hand, the Caries Spectrum and Treatment (CAST) Index was developed to combine both ICDAS II and PUFA (Frecken et al. 2011), but this resulted in a complex index with ten codes.

Other than indices, more accurate measurements such as radiographs were sometimes used as a screening tool for pulpal and periapical diseases. In fact, radiological assessment is crucial because chronic apical periodontitis often develops without subjective symptoms (Huumonen & Ørstavik 2002). However, there is no standard criteria for the registration of apical periodontitis in surveys and epidemiological study, either for periapical radiographs or panoramic radiographs. This makes comparison between studies difficult. With the validated Periapical Index (PAI), calibrated observers could use it for such purpose (Huumonen & Ørstavik 2002). Nevertheless,

periapical and panoramic radiographs were reported with high specificity (0.98 and 1.00, respectively) but low sensitivity (0.55 and 0.28, respectively) when compared against CBCT (Estrela et al 2008). Hence, the use of these conventional imaging tends to detect only advanced lesions and therefore underestimate disease prevalence.

Apart from the issue of accuracy, the use of panoramic radiographs were controversial, especially in striking a balance between increased radiation exposures, cost to the health care system and diagnostic yield (Rushton et al. 2001). Panoramic radiographs, in combination with a limited number of intra-oral radiographs, yield good diagnostic information with low radiation dose (Molander et al 1993). Therefore, many dentists reported using it for screening oral diseases in new patients (Rushton et al 1999). Although many radiological findings could be observed on panoramic radiographs, Rushton et al. (2001) argued against its use because the findings are also revealed on bitewing radiographs, or are often not contributive towards treatment planning.

Problem Statement

The PUFA index complements the widely used DMFT index by recording the advancement of the caries lesion into surrounding tissues, which includes pulpal involvement (P), ulceration due to tooth fragments (U), fistula formation (F) and abscess (A). However, this new index has yet to be validated, hence limits its use in prevalence study. On the hand, despite the importance of radiological diagnosis, screening pulpal and periapical diseases using panoramic radiographs (orthopantomographs OPG) are plagued with issues of accuracy and radiation risk. Therefore, comparison of the two screening methods, using PUFA index or panoramic radiograph, will inform clinicians and researchers in selecting the appropriate tool for screening pulpal and periapical diseases.

Research Questions

- a. How reliable is the PUFA in screening pulpal and periapical diseases?
- b. How reliable is the PAI in screening pulpal and periapical diseases?
- c. How accurate is the PUFA in screening pulpal and periapical diseases?
- d. How accurate is the PAI in screening pulpal and periapical diseases?
- e. Is there a difference in the accuracy of PUFA and PAI in screening pulpal and periapical diseases?

Hypotheses

- a. The PUFA index is highly reliable in screening pulpal and periapical diseases.
- b. The PAI is highly reliable in screening pulpal and periapical diseases.
- c. The PUFA index is highly accurate in screening pulpal and periapical diseases.
- d. The PAI is highly accurate in screening pulpal and periapical diseases.
- e. There is a difference in the accuracy of PUFA and PAI in screening pulpal and periapical diseases.

Research Objective

General Objective:

To evaluate the reliability and accuracy of PUFA and PAI in screening for clinical outcomes of untreated caries, specifically pulpal and periapical diseases.

Specific Objectives:

- a. To determine the intra- and inter-examiner reliability of PUFA in screening pulpal and periapical diseases.
- b. To determine the intra- and inter-examiner reliability of PAI in screening pulpal and periapical diseases.
- c. To determine the sensitivity, specificity and predictive values of PUFA in screening pulpal and periapical diseases.
- d. To determine the sensitivity, specificity and predictive values of PAI in screening pulpal and periapical diseases.
- e. To compare the accuracy of PUFA and PAI in screening pulpal and periapical diseases.

Methods

Participants

The study will be carried out in Primary Care Clinic, Univeristi Kebangsaan Malaysia. Consecutive sampling will be used, all eligible patients are invited to participate. The inclusion criteria are as follow:

- i. New patient, not receiving active dental treatment at the time of the study
- ii. Adult patient (18 years old or above)
- iii. Has at least 12 teeth in the oral cavity
- iv. Presented with the clinical situation for which radiograph(s) were indicated (American Dental Association 2012)
- v. No radiograph was taken within the last 6 months

At the time of this study, the UKM dental clinic routinely ordered OPG for patients with multiple dental problems, particularly if they need periodontal, prosthodontic, orthodontic treatment or oral surgery. Hence, only patients who required OPG according to the screening procedure of this institution is included. Pregnant or medically compromised patients (American Society of Anesthesiologists ASA3) will be excluded.

Sample size is estimated using the method described in Buderer (1996). Based on the systematic review, the prevalence of periapical radiolucency was about 5% (Pak et al 2012). As there was no prior data, the sensitivity of PUFA was assumed conservatively at 0.50 and specificity at 0.80. Therefore, a total of 1921 and 65 teeth are required, based on the assumed sensitivity and specificity, respectively. Since each patient must have at least 12 teeth, 161 patients will be sufficient for estimation of both sensitivity and specificity. Assuming 2% of the radiographs have

overlapped images, poor contrast or poor quality, the sample size was adjusted to a total of 165 patients.

The unit of interest for analysis is at tooth level. A tooth is considered present in the mouth when any part of it was visible. The teeth excluded for scoring are unerupted teeth, congenitally missing teeth or supernumerary teeth, teeth removed for reasons other than dental caries, and primary teeth retained in the permanent dentition.

Reference Standard

The reference standard is the clinical diagnosis. This will be carried out by an endodontic postgraduate student, using the diagnostic criteria of AAE. Comprehensive examination will be carried out for each tooth, followed by investigation using OPG, periapical radiograph, periodontal probing, heat test, cold test, electric pulp tester when indicated, to aid in arriving at the definitive diagnosis. To observe the As Low As Reasonably Achievable (ALARA) principle, additional periapical radiographs were taken only when radiographic assessment is impossible with the OPG because of overlapping, blurred images or obscured periapical region. Because OPG has lower sensitivity than periapical radiograph in detecting apical periodontitis, periapical radiograph is also taken when periapical lesion cannot be seen on OPG but a tooth is having large caries or showing signs and symptoms of pulpal and periapical diseases. At the end of this comprehensive examination, each tooth will have pulpal and apical diagnoses.

Index Test 1: PUFA

Two independent, trained dentists are employed to screen the participants using DMFT and PUFA indices, blinded to the clinical diagnosis and PAI scoring. The examination is done using only a mouth mirror. Each tooth was scored either Decayed, Missing or Filled.

If the tooth is present, PUFA scoring is done. A particular tooth can be scored as either one of Normal, Pulpal involvement, Ulceration, Fistula or Abscess. In case of doubt concerning the extent of odontogenic infection, the basic score (Pulpal involvement) is given. Lesions in the surrounding tissues that are not related to a tooth with visible pulpal involvement as a result of caries are not recorded.

Index Test 2: PAI

The OPG will be taken for all participants by qualified radiographers using Sirona Orthophos (Sirona Dental System GmbH, Bensheim, Germany). All radiographs will be evaluated by two trained dentists, blinded to the clinical diagnoses and the PUFA scoring. Each tooth is scored for the periapical status using the Periapical Index (PAI) proposed by Ørstavik et al (1986).

Ethical consideration

Ethics approvals will be obtained from the research ethics committee of the university. The research will be conducted in accordance with the Declaration of Helsinki. Informed consent will be obtained from all participants in written form. Emergency treatment will be carried out if the patient is in pain or showing sign of systemic spread of infection (e.g. swelling, fever). Following the study, all participants will be arranged for appropriate treatment.

Data analysis

The demographic data of the patients will be analyzed using descriptive statistics. Mean DMFT and PUFA scores will be calculated. The assessment of the teeth will be tabulated.

The pulpal diagnosis and apical diagnosis for each tooth will be dichotomized as Disease or No Disease. To determine the accuracy of the test, the outcome of PUFA is dichotomized as Positive ($PUFA > 0$) or Negative ($PUFA = 0$) for each tooth. Similarly, the PAI was dichotomized as Positive ($PAI \geq 3$) or Negative ($PAI < 3$). Intra- and inter-examiner reliability will be determined using Cohen's kappa. Sensitivity, specificity, positive predictive value and negative predictive value will be calculated. To compare the two index tests, ROC contrast estimation will be computed.

References

- Fejerskov O, Kidd EAM (2003) Dental caries: the disease and its clinical management. Second Edition, Denmark. Blackwell Monksgaard.
- Oral health division, Ministry of Health Malaysia (2011) National Oral Health Plan for Malaysia 2011–2020.
- Figueiredo MJ, de Amorim RG, Leal SC, Mulder J, Frencken JE (2011) Prevalence and severity of clinical consequence of untreated dentine carious lesion in children from a deprived area in Brazil. *Caries Research* **45**, 435–42.
- Petersen PE. The World Oral Health Report (2003) Continuous improvement of oral health in the 21st century –the approach of the WHO Global Oral Health Programme. *Community Dentistry Oral Epidemiology* **15**, 3–24
- Larmas M (2010) Has dental caries prevalence some connection with caries index values in adults? *Caries Research* **44**, 81–4.

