Appendix 1. Flow chart

Appendix 2. Dummy tables

A total of x patients were invited to participate.

X fulfill the inclusion criteria.

X declined to participate because

Table 1. Demographic distribution of the patients examined

	Count (%)	Mean (SD)
Total number of patient assessed		
Gender		
Male		
Female		
Age		
Age		
DMF		
Decayed		
Missing		
Filled		
DMFT		
DMFT > 0		
PUFA		
Pulpal involvement		
Ulceration		
Fistula		
Abscess		
PUFA		
PUFA > 0		

Table 2. Distribution of teeth assessed using DMFT, PUFA, PAI, Pulpal Diagnosis and Periapical Diagnosis

	Count	Percent
Total number of teeth assessed		
DMFT		
Decayed		
Missing		
Filled		
PUFA		
Pulpal involvement		
Ulceration		
Fistula		
Abscess		
PAI		
1		
2		
3		
4		
5		
Pulpal diagnosis		
Normal pulp		
Reversible pulpitis		
Symptomatic irreversible pulpitis		
Asymptomatic irreversible pulpitis		
Pulp necrosis		
Previously treated tooth		
Previously initiated therapy		
Apical diagnosis		
Normal apical tissue		
Symptomatic apical periodontitis		
Asymptomatic apical periodontitis		
Chronic apical abscess		
Acute apical abscess		
Condensing osteitis		

Table 3. Intra- and inter-examiner reliability (Cohen's kappa) of DMFT, PUFA and PAI

	DMFT	PUFA	PAI
Intra-examiner reliability 1			
Intra-examiner reliability 2			
Inter-examiner reliability			

Table 4. Accuracy of PUFA and PAI

	Gold Standard = Pulpal Diagnosis		Gold Standard = Periapical Diagnosis	
	PUFA	PAI	PUFA	PAI
TP				
FN				
TN				
FP				
Sensitivity				
Specificity				
PPV				
NPV				

Table 5. ROC contrast estimation

Gold Standard	Contrast	Estimate	SE	95% Wald Confidence Limits		Chi-square	P
				Lower	Upper		
Pulpal diagnosis	PUFA-PAI						
Periapical diagnosis	PUFA-PAI

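### The apical reference rests on radiographs that the protocol says miss early lesions, so apical NPV is probably overstated and the accuracy claims need a narrower target

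*Protocol*

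**What the plan says.** - **Introduction.** Periapical and panoramic films are credited with high specificity (0.98 and 1.00) but "low sensitivity (0.55 and 0.28, respectively) when compared against CBCT". The conclusion drawn is: "Hence, the use of these conventional imaging tends to detect only advanced lesions and therefore underestimate disease prevalence". The same paragraph notes that "chronic apical periodontitis often develops without subjective symptoms".
- **Reference Standard.** The reference is a clinical diagnosis made for each tooth by an endodontic postgraduate student. The examination is "followed by investigation using OPG, periapical radiograph, periodontal probing, heat test, cold test, electric pulp tester when indicated, to aid in arriving at" the final diagnosis. A periapical film is added where the OPG cannot be read, or where an OPG-negative tooth has large caries or signs or symptoms. CBCT is not used.
- **Data analysis.** "The pulpal diagnosis and apical diagnosis for each tooth will be dichotomized as Disease or No Disease". Sensitivity, specificity, PPV and NPV of PUFA and PAI are then computed against that result.
- **Appendix 2, Table 4.** The apical columns are headed "Gold Standard = Periapical Diagnosis". Objectives and hypotheses c to e speak of periapical disease without restriction.

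**The concern.** The Introduction says that conventional films miss many apical lesions and that such lesions are often silent. A silent lesion that shows on no film will usually be recorded as normal apical tissue. In the apical columns of Table 4 it then counts as No Disease, and as a true negative if the index test is also negative.

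NPV is the figure that would support using PUFA or PAI to decide that a tooth needs no further work-up, which is the screening and triage use the protocol has in mind. If it is inflated, hypotheses c and d could be supported for conventionally detectable disease while the text claims periapical disease in general.

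**Working it through.** **Inputs.** From the sample-size paragraph under Participants: prevalence of periapical radiolucency 5%, PUFA sensitivity 0.50, specificity 0.80. From the Introduction: the film sensitivities and specificities above. Because the 5% is a prevalence of radiolucency, it is read here as observed prevalence.

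**The plan's own figures.** With z = 1.96 and half-width 0.10 (neither is stated; this half-width fits), 3.8416 × 0.25 / (0.01 × 0.05) = 1920.8, so 1921 teeth. Likewise 3.8416 × 0.16 / (0.01 × 0.95) = 64.7, so 65 teeth. Then 1921 / 12 gives 161 patients, and 161 / 0.98 gives 165. The sample size reproduces and is not at issue.

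**NPV as Table 4 would show it.** Test-negative share = 0.95 × 0.80 + 0.05 × 0.50 = 0.785. NPV = 0.76 / 0.785 = 0.968.

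**NPV allowing for missed lesions.** Let r be the sensitivity of the whole reference and q the PUFA-positive rate among missed lesions. Assume reference specificity 1.

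- Missed lesions, as a share of all teeth: m = 0.05/r − 0.05
- True NPV = 1 − [0.025 + m(1 − q)] / 0.785
- True sensitivity = 0.50r + q(1 − r)

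| r | m | NPV, q = 0.20 | NPV, q = 0.50 | Sensitivity, q = 0.20 | Sensitivity, q = 0.50 |
|---|---|---|---|---|---|
| 0.80 | 0.0125 | 0.955 | 0.960 | 0.44 | 0.50 |
| 0.55 | 0.0409 | 0.926 | 0.942 | 0.365 | 0.50 |
| 0.28 | 0.1286 | 0.837 | 0.886 | 0.284 | 0.50 |

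Here q = 0.20 is the non-diseased rate and q = 0.50 the detected-lesion rate. The last row is an extreme in which the clinical tests and the added films contribute nothing. If 5% were instead the true prevalence, then with q = 0.50 and r = 0.55 the apparent NPV would be 1 − 0.025 × 0.55 / 0.785 = 0.982 against a true 0.968. The direction is the same.

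**PAI sensitivity.** Take the panoramic sensitivity of 0.28 as a stand-in for PAI, and assume that the reference finds every lesion visible on the OPG. If the films lift the reference to 0.55, apparent PAI sensitivity is 0.28 / 0.55 = 0.51. If the reference rests on the OPG alone, it is 0.28 / 0.28 = 1.00.

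**What the 0.98 specificity does.** Suppose every tooth had a periapical film (sensitivity 0.55, specificity 0.98), at true prevalence 5% and with errors independent of PUFA:

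- Apparent true positives = 0.025 × 0.55 + 0.19 × 0.02 = 0.01755
- Apparent false negatives = 0.025 × 0.55 + 0.76 × 0.02 = 0.02895
- Apparent sensitivity = 0.01755 / 0.0465 = 0.377, against a true 0.50
- Apparent NPV = 1 − 0.02895 / 0.785 = 0.963, against a true 0.968

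Both are then understated. The share of healthy PUFA-negative teeth that would need a film to cancel the NPV bias is 0.05 × 0.50 × (1 − r) / (0.95 × 0.80 × 0.02). That is 74% at r = 0.55 and 33% at r = 0.80. For PAI at r = 0.55 it is 0.05 × 0.72 × 0.45 / (0.95 × 0.02) = 85%.

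**The case against.** Four points can be made for the plan.

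1. *The image sensitivities are not the sensitivity of the reference.* The reference also uses examination, probing and pulp tests, and suspicious OPG-negative teeth get a film. This stands: 0.28 to 0.55 describes the images, and the figure for the combined reference is unknown. The direction of the NPV bias remains at 80%, but the size is an assumption.
2. *Film false positives push the other way.* This stands too. A reader might infer that the Table 4 NPV is a guaranteed upper limit, or that the bias would persist with a film on every tooth. The protocol's own specificity of 0.98 contradicts both. Under the stated imaging rule, however, films on 74% of healthy PUFA-negative teeth look implausible.
3. *The comparator is already stated.* The Introduction speaks of testing the index against the usual clinical procedures, and the Reference Standard section says the reference is clinical and acknowledges the weakness of the OPG. That supports the narrower target, but the hypotheses, objectives and table headings do not carry it.
4. *A sensitivity table may sit in an SAP that is not shown.* That is possible. The unrestricted claims and the gold-standard label are fixed in the protocol itself.

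**Conclusion.** The point holds in a limited form. With few periapical films and reference specificity near 1, apical NPV is probably optimistic. For PUFA, the share of test-negative teeth that carry disease would be 4.0% to 4.5% (reference finding 80% of lesions) or 5.8% to 7.4% (55%), where Table 4 would show 3.2%. These figures rest on 5% being the observed prevalence and on a reference sensitivity that the protocol does not give.

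A reader might also infer that all the apical sensitivities are inflated by missed lesions. The document does not support that. For PUFA there is no such bias if missed lesions are test-positive as often as detected ones. For PAI an upward bias is likely, but largely because PAI is read on the OPG that also feeds the reference.

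**What to change.** 1. In objectives and hypotheses c to e, and in the headings of Tables 4 and 5, define the apical target as apical disease detectable by clinical examination and conventional radiographs. Limit the conclusions to that target.
2. Under Data analysis, add one pre-specified sensitivity table computed from the planned 2x2 counts. It recomputes apical sensitivity and NPV for reference sensitivity from 0.28 to 1.00 and reference specificity from 0.98 to 1.00. The test-positive rate among missed lesions runs from the non-diseased rate to the detected-lesion rate for PUFA, and from 0 to the non-diseased rate for PAI.
3. Describe the Table 4 apical NPV as probably optimistic when reference specificity is near 1, without calling it an upper limit.

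The cost is some wording and one table. Imaging, patients and readers do not change. The downside is that the apical claims become narrower.

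### The tooth-level PUFA-PAI ROC contrast makes no provision for 12 or more teeth per patient; if test errors correlate within a mouth, its SE, limits and P are too optimistic

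*Protocol*

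**What the plan says.** - **Unit.** The end of Methods, Participants states: "The unit of interest for analysis is at tooth level". Inclusion criterion iii reads: "Has at least 12 teeth in the oral cavity".
- **Hypothesis (e).** "There is a difference in the accuracy of PUFA and PAI in screening pulpal and periapical diseases".
- **Comparison.** Data analysis dichotomises PUFA (above 0) and PAI (3 or more) for each tooth, then states: "To compare the two index tests, ROC contrast estimation will be computed".
- **Output.** Appendix 2, Table 5 has one PUFA-PAI row for each gold standard (pulpal, periapical). Its columns are estimate, SE, "95% Wald Confidence Limits", chi-square and P. Table 4 lists accuracy measures without limits or tests, so Table 5 is the only inference on hypothesis (e).
- **Sample size.** Participants derives 1921 teeth for sensitivity and 65 for specificity, then concludes: "Since each patient must have at least 12 teeth, 161 patients will be sufficient for estimation of both sensitivity and specificity". A 2% allowance for poor radiographs brings the total to 165.

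The protocol nowhere mentions clustering, a design effect, a robust variance, a patient random effect or patient-level resampling.

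**The concern.** All teeth of a patient share the same mouth, the same mirror-only PUFA examination and the same OPG. A film that is blurred or overlapped can mislead the PAI reader on several teeth at once, and an examiner may be lenient or strict throughout one mouth. Test errors may therefore correlate within patients.

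The protocol does not name the variance estimator, but a standard tooth-level ROC contrast treats teeth as independent. With positively correlated errors, the real variance of the contrast then generally exceeds the estimated one. The Table 5 limits would be too narrow, P too low, and a difference between PUFA and PAI would be declared too often. Sensitivity, specificity and predictive values as point estimates (objectives c and d) do not depend on this.

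**Working it through.** **1. The plan's own figure.** Inputs from Participants are prevalence 0.05, sensitivity 0.50 and specificity 0.80. A two-sided 95% level and half-width d = 0.10 are not stated. They are inferred because they return both tooth counts (d = 0.05 would give 7683 and 259).

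- Sensitivity: 1.96² × 0.50 × 0.50 / 0.10² / 0.05 = 1920.8, so 1921 teeth.
- Specificity: 1.96² × 0.80 × 0.20 / 0.10² / 0.95 = 64.7, so 65 teeth.
- Patients: 1921 / 12 = 160.1, so 161; 161 / 0.98 = 164.3, so 165.

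All four figures reproduce, and no design effect enters. This is a precision calculation for sensitivity and specificity, not for the contrast, but it shows how the plan counts teeth.

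**2. The contrast and its tooth-level SE.** For a binary test AUC = (Se + Sp)/2, so the contrast is (Se₁ + Sp₁ − Se₂ − Sp₂)/2. With 165 × 12 = 1980 teeth, 99 are diseased and 1881 are not. Take both tests at 0.50/0.80 with errors independent between tests:

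SE = ½ × √(2 × 0.25/99 + 2 × 0.16/1881) = ½ × √(0.00505 + 0.00017) = 0.036.

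The sensitivity term dominates. A mouth has on average only 12 × 0.05 = 0.6 diseased teeth, so the inflation is smaller than the textbook 1 + 11 × ICC.

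**3. Simulation with clustering.** Beta-binomial model, 165 patients, 5% disease, both tests at 0.50/0.80 (true contrast 0), one assumed ICC for disease and test errors, errors independent between tests, 10,000 replicates per cell.

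| Assumed ICC | Rejection, 12 teeth | True/naive SE, 12 teeth | Rejection, 24 teeth | True/naive SE, 24 teeth |
|---|---|---|---|---|
| 0 | 4.9% | – | 5.0% | – |
| 0.05 | 5.8% | – | 6.6% | – |
| 0.1 | 7.0% | 1.08 | 10.1% | 1.19 |
| 0.2 | 12.0% | 1.25 | 19.0% | 1.48 |
| 0.3 | 19.3% | 1.47 | 29.0% | 1.84 |

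The columns agree: with SE ratio r, rejection is 2[1 − Φ(1.96/r)]. For 12 teeth this gives about 7.0%, 11.7% and 18.2% at r = 1.08, 1.25 and 1.47. A patient-clustered variance (sum of squared patient-level residuals) gave 5.2-7.8% throughout.

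**4. A different correlation model.** With latent-normal correlation (2,000 runs per cell) of 0.1, 0.3 and 0.5 for errors, and 0 to 0.5 for disease, tooth-level rejection was 6-8%, 9-12% and 12-20% at 12 teeth, and 7-11%, 13-22% and 17-29% at 24 teeth. The clustered variance gave about 5-8%.

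**5. Where the effect shrinks or persists.**

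- Only disease clusters: 4.9-5.6%, no material inflation.
- Only test errors cluster (ICC 0.1-0.3): 6.3-8.6% at 12 teeth, 7.4-11.4% at 24.
- Patient effects correlate 0.5 between the tests (6,000 replicates; ICC 0.1, 0.2, 0.3): 6.6%, 9.5%, 13.9% at 12 teeth; 7.8%, 13.4%, 21.3% at 24. If the effects are identical, about 5%.
- Teeth in a mouth share only a tendency to score positive and disease does not cluster: errors in sensitivity and specificity offset, and the variance ratio is 1.00-1.05 (12 teeth) or 1.00-1.14 (24). With latent disease correlation of 0.3-0.5 it rises to 1.07-1.69 and 1.12-2.65.
- PAI set at the panoramic accuracy quoted in the Introduction (0.28/1.00): non-coverage of the Table 5 limits at ICC 0.1, 0.2 and 0.3 is 7.6%, 11.9%, 18.4% (12 teeth) and 9.4%, 18.7%, 28.5% (24).

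**The case against.** The protocol names no variance estimator. A patient-clustered ROC variance would fill the same Table 5 columns, the choice could be left to an SAP, and a tooth-level unit does not by itself imply an independence variance. That is fair as far as the wording goes. But the protocol fixes the unit, the method and the form of the output, and its only worked calculation counts every tooth as independent. Nothing points the analyst to any other variance.

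The sample size also has slack if patients have more than 12 teeth: 24 teeth each would give 165 × 24 = 3960, or 2.06 times the 1921 required. This helps the precision of sensitivity but not the contrast, where the tooth-level SE becomes more wrong as clusters grow.

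The largest rejection rates need an ICC of 0.3 for disease and errors together, with independent patient effects between the tests. At 12 teeth and ICC 0.1 the true SE is only 8% above the naive one, and a purely shared tendency to score positive does almost no harm unless disease clusters too. These limits stand and are why the claim is conditional.

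Two smaller points also stand. Table 5 will give two P values and the protocol states no significance level, so the 5% used here is the conventional one. And the clustered variance is itself slightly liberal: under disease-only clustering it reached 7.0% where the naive test stayed at 4.9-5.6%.

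**Conclusion.** The concern holds. The single planned comparison of the two tests has no provision for clustering, and the written design treats teeth as independent. That the provision is absent is certain; the size of the effect is not, because the documents give no within-patient correlation. At ICC 0.05-0.1 the nominal 5% test would run at about 6-7% with 12 teeth per patient and 7-10% with 24; at ICC 0.2-0.3, at 12-19% and 19-29%. These figures assume 5% prevalence (the protocol's figure for periapical radiolucency; it gives none for pulpal disease), equal ICC for disease and errors, and no correlation of patient effects between tests. Relaxing the last two lowers them, in some settings to nominal. In no setting with correlated errors was the tooth-level SE materially too large, so the risk runs one way. It should be fixed, but it does not threaten the point estimates.

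**What to change.** Keep tooth-level scoring and tooth-level point estimates. Add one sentence to Data analysis: the SE, 95% limits, chi-square and P in Table 5 are computed with a ROC variance for clustered data, with the patient as cluster, or by a bootstrap that resamples patients. Say that the same patient-clustered method applies to any interval later reported for sensitivity, specificity, predictive values or kappa; Tables 3 and 4 plan none at present.

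The cost is that sentence and a few lines of code, with no new data. If errors cluster, the Table 5 limits become wider. If they do not (ICC 0, or clustering of disease alone), the clustered test still ran at 5.2-7.0%, so little is lost.
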